# ***Ultrasound-guided peripheral IV vs. standard technique in difficult vascular access patients by ICU nurses.***

## ***“Research Protocol”***

### ***1-Introduction:***

Peripheral intravenous access is one of the most common and most important invasive procedure performed by ICU nurses. The importance of being able to insert an IV quickly, successfully and with little discomfort cannot be overestimated. Establishing good peripheral access is essential in ICU because this allows timely administration of fluid and medication and also allow early discontinuation or even avoidance of central line when there are no specific indications for their use.

Failure in establishing good peripheral access is a very frequent problem in ICU because of the high prevalence of chronic illness, peripheral edema, obesity and for many other reasons. Multiple attempts in establishing IV access in difficult IV access (DIVA) patients frequently lead to a high level of patient discomfort and nurse's frustration. Peripheral IV cannulation can be incredibly time intensive for nurses when patients are DIVA. Furthermore, failure of peripheral intravenous cannulation (PIVC) in ICU setting frequently leads to insertion of a central line or PICC which are associated with more risk of catheter-associated infection and other serious complications [1].

Using Ultrasound to guide central line insertion is the standard of care but ultrasound-guided PIVC in difficult patients remained poorly utilized rescue tool despite its potential advantages in the ICU setting. Ultrasonographic guidance may improve the rate of successful PIVC in patients who have been historically difficult to access, leading to less time spent obtaining intravenous access and greater patient satisfaction.

In difficult IV access patients, we hypothesize that ultrasound-guided peripheral intravenous cannulation (USG-PIVC) increases the success rate of peripheral IV access in difficult IV access ICU patients. In addition, we hypothesize the USG-PIVC is a very safe procedure and is associated with very few minor complications.

## **2- Literature review:**

Ultrasound-guided central venous access has been well studied throughout the past few decades, several studies showed an increased success rate and decreased complications compared to the traditional landmark approach [2].

Ultrasound-guided peripheral intravenous cannulation (USG-PIVC) is a technique that can be utilized in patients with difficult peripheral IV cannulation which is a frequent problem encountered in ICU. There are multiple factors associated with failure in establishing peripheral IV access in adults, e.g., obesity, IVDU, DM, nurse's experience and poor peripheral venous visibility and palpability [2,3]. James CR et al. found that clinical gestalt is an excellent predictor in determining the probability of PIVC first-time insertion success or failure. He suggested that clinical gestalt can prospectively stratify patients into groups according to their risk of PIVC placement failure [3].

There are multiple small studies in the emergency literature which found that UG-PIVC by ED physician and nurses in DIVA patients can lead to better success rate, few punctures and greater patient satisfaction compared with traditional landmark technique. In a prospective observational study by Brannam et al., he demonstrated that emergency nurses could be trained to use US-guided PIV access with high success rates and few complications [5]. In another small prospective randomized trial in ED, the superiority of ultrasound-guided peripheral intravenous cannulation was not supported. The investigators found that ultrasound-guided peripheral intravenous cannulation did not decrease the number of attempts or the time to successful catheterization, nor did it improve patient satisfaction compared with the group that did not use ultrasonography [6].

In another small randomized prospective study conducted in an emergency department in 2005, Costantino et al found that ultrasound-guided IV cannulation performed by emergency physicians are more successful than traditional “blind” techniques, requires less time, decreases the number of percutaneous punctures, and improves patient satisfaction in patients with difficult I.V access [7]. In a recent single-center randomized prospective study in ED, nurses were found to be more successful in obtaining IV access using US guidance than palpation technique in difficult access patients. Nurses using US-guided technique had a higher success rate of 76% in placing a functional IV compared to 56% using the standard palpation technique [8].

In a single-center retrospective study, a single physician attempt in placing peripheral IVs using ultrasound in difficult cannulation ICU patients found that first attempt success rate was 77% with 99% overall success rate. As a result of placing these PIV catheters, 40 central lines were discontinued, and 34 central lines were avoided. This study has a limitation because it is a retrospective study examining a single physician's experience with the technique [9]. In another

small ICU RCT, the ultrasound-guidance technique was more successful without increasing cannulation time despite the use of additional equipment [10].

In a recent systematic review published in 2016, the authors found that the ultrasound-guided technique improves the success rate of intravenous access significantly (OR = 3.00, p < .0001) and decreased the number of attempts in the overall group of difficult intravenous-access patients [11].

Ultrasound-guided peripheral IV cannulation has a steep learning curve. Stoltz La found that new learners of the procedure are capable of a greater than 70% success rate after placement of four USG PIVCs. A success rate of greater than 88% is achieved after 15 to 26 attempts [12]

There are multiple factors associated with a high failure rate and shorter catheter survival when USG-PIVC is used. In the study conducted by Michael D et al., he found that veins less than 3 mm in diameter or greater than 1.5 cm in depth were associated with high failure rate [13]. In another study conducted by J. Matthew et al., he found 2 important factors associated with short catheter survival when performed with ultrasound guidance. Deep veins (depth > 1.2 cm) and proximal location were associated with early catheter failure when they are performed with ultrasound-guided technique [14].

Based on many previous studies [6,13,15], complication rate associated with USG-PIVC is the same as traditional blind techniques. Adhockery et al. found that the infection rate of USG-PIVC is the same as a blind technique [14]. Thomas G et al. reported no significant complications in their RCT in USG-PIVC group

### **3. Methodology**

#### **3.1. Study design:**

This is a randomized controlled single-site trial with two groups in a parallel design. In this study, we will compare the success rate of ultrasound-guided peripheral intravenous access (experimental group) to a traditional landmark approach (control group) in patients with DIVA. It is a non-blinded study because of the nature of the intervention.

#### **3.2. Setting :**

This study will be conducted in the adult intensive care unit of Kingston general hospital which is an urban university teaching hospital with 33 ICU beds and more than 1000 ICU admissions per year.

#### **3.3. Study population:**

A convenience sample of ICU patients with difficult cannulation will be selected and enrolled in this study. Difficult cannulation is defined as poorly visible and palpable upper extremities veins due to any cause after two failed attempts using traditional technique. All consecutive patient with difficult cannulation will be assessed for enrolment in this study starting from December 2018 till May 2019. A research assistant will be available for patient enrollment and data collection between 8:00 AM till 5:00 PM during weekdays.

#### **3.4. Inclusion / exclusion criteria**

Inclusion Criteria:

- 18 years of age or older
- DIVA patients after two failed attempts

Exclusion Criteria:

- Upper-extremity cellulitis
- Unstable and need urgent intravenous access (central line or IO).

### ***3.5. Study procedure***

The study will be conducted in two phases. Phase one will involve education and training of a cohort of nurses to perform US-guided PIVC. Experienced ICU nurses with two years of experience will be recruited to participate in the study. All nurses will have no prior experience in USG-PIVC prior to this study. Education consists of didactic two hours lecture and hands-on practice on synthetic training models (blue phantoms). This will cover basic machine operation, image optimization, sonographic anatomy and ultrasound techniques for guiding PIVC. This will be followed by 2-3 months observation period during which nurses have to perform at least 15 successful ultrasound-guided PIVC on live subjects before actual patients' enrolment. Phase two involved patient enrolment of difficult peripheral access ICU patients meeting specific inclusion and exclusion criteria. Patients will be systematically randomized to the ultrasound-guided or the landmark technique (control) using envelop randomization.

Only upper limb veins will be selected for cannulation. All the cannulation will be done under semi aseptic technique as per standard PIV placement and cleaning procedures. USG-PIVC will be performed using sterile gel for the

procedure, and the ultrasound probe will be covered with sterile adhesive films (e.g., 3M Tegaderm). Two already available departmental ultrasound machines (sonosite edge ) will be used for this study. High-frequency probe (5-10 MHz) with single operator out of plane (short access) approach will be used for ultrasound-guided cannulation.

When using USG-PIVC, veins deeper than 1.5 cm from the skin surface and veins with diameter less than 0.3 cm will be avoided because of high failure rate and increased risk of extravasation. Catheter length and size will be selected based on the depth and size of veins to ensure that a sufficient portion of the catheter will remain in the vessel to prevent early failure.

### **3.6: *outcome measures:***

#### **Primary outcome measure:**

- Successful cannulation by ICU nurses.

#### **Secondary outcome measures:**

- Number of punctures attempted.
- 24 hours catheter survival.
- Complications (cellulitis ,phlebitis arterial puncture, nerve injuries, infiltration, hematoma formation).
- Subsequent need for PICC or central line.

### **3.7. Data collection and processing**

Intensive care nurses participating in the study will record all the data related to outcome measures on a preprinted data collection forms in real time. The raw data will be entered by investigators into SPSS software for analysis.

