### ***3.8. Data analysis***

An intention-to-treat analysis will be performed. Using the power of 80% and alpha of 0.05, the sample size was calculated to be 25 per group. Categorical variables such as success rate, catheter survival rate and complication rate will be presented as a percentage and will be compared using Fisher exact tests. Continuous variables such as insertion time and the number of attempts will be shown as mean, median (with interquartile ranges), and 95% confidence interval (CI) and will be compared using Mann-Whitney U tests. All statistical analysis will be conducted using IBM SPSS Base 25 for Windows.

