### ***4. Definitions:***

Difficult IV access patient is defined as failure of 2 attempts to cannulate upper limb veins in patients with invisible or non-palpable veins after application of a tight proximal tourniquet. Successful cannulation is defined as the ability to aspirate blood and ability to flush the cannula without resistance to the flow and without evidence immediate extravasation.

Failure PIVC is defined as extravasation with initial infusion or inability to withdraw blood. Failed cannulation is defined as failed three attempts excluding the initial two attempts which are part of the definition of difficult venous cannulation. Time will be recorded in minutes in real time by the ICU nurse with time zero defined as the first skin puncture after patient randomization in the study.

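### In an open trial, the plan lets the cannulating nurse record their own success, puncture count and time, although a research assistant is already available for data collection

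*Protocol*

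**What the plan says.** - **Blinding.** Protocol section 3.1: "It is a non-blinded study because of the nature of the intervention".
- **Who records outcomes.** Section 3.7: "Intensive care nurses participating in the study will record all the data related to outcome measures", in real time on preprinted forms. The investigators' stated part is to enter the raw data into the software.
- **Who cannulates.** Section 3.5: "Experienced ICU nurses with two years of experience will be recruited to participate in the study". These are the nurses trained in the ultrasound technique, which is done by a single operator.
- **Who records time.** Section 4 assigns this to the ICU nurse, starting at the first skin puncture after randomization.
- **What is recorded.** The primary outcome is "Successful cannulation by ICU nurses" (section 3.6). Secondary outcomes include "Number of punctures attempted". Section 3.8 also compares "Continuous variables such as insertion time and the number of attempts".
- **How success is judged.** Section 4 requires that blood can be aspirated, and also "ability to flush the cannula without resistance to the flow and without evidence immediate extravasation".
- **The assistant.** Section 3.3: "A research assistant will be available for patient enrollment and data collection between 8:00 AM till 5:00 PM during weekdays". No outcome task is named.

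**The concern.** In an open trial, the person with most influence over a bedside outcome, and the clearest view of the allocation, is the operator. Here the nurses who record outcomes are described in the same terms as the nurses who cannulate, and no sentence separates the two roles or provides for a check.

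Three compared measures are exposed: success, number of punctures and insertion time. The first two are linked, because section 4 defines failed cannulation as three failed attempts after the two that qualified the patient. An uncounted puncture can therefore affect both. Time has a practical difficulty as well: the clock starts at a moment when a single operator has both hands occupied.

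If recording error differs between arms, the comparison shifts. It could favour ultrasound or count against it. The protocol does not say who performs the landmark cannulations, so the direction cannot be inferred from the text.

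**Working it through.** **Step 1: reading the sections together.** Sections 3.3 and 3.7 can both be true: an assistant may collect some data while nurses record outcomes. This is not a contradiction. Sections 3.5 and 3.7 describe operators and recorders as nurses participating in the study. Section 4 says only that the ICU nurse records time. The text does not say that the operator fills in the form, and it does not rule it out.

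**Step 2: what an observer could add.** Punctures, start and stop times, aspirated blood, a completed flush and visible extravasation can all be seen. Resistance to flush is felt only by the operator.

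**Step 3: how much error would matter for the primary outcome.** The plan gives no figure to reproduce on this point, so this is an illustration.

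*Inputs from the protocol:* 25 per arm, alpha 0.05 and Fisher's exact test (section 3.8); 56% success with standard technique, from the nurse-performed emergency department trial in the literature review (section 2).

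*Assumptions:* a two-sided test; 56% as the true rate, with 40% and 70% as the range; every error rate *m*, the share of true failures scored as successes.

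*Formula:* recorded success = p + (1 − p) × m in each arm. The rejection probability is the sum, over all pairs of binomial counts with n = 25 per arm, of the probability of each pair with Fisher p ≤ 0.05. At p = 0.56, m = 10, 20 and 30% adds 0.44 × m = 4.4, 8.8 and 13.2 points.

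Probability of a significant result when the true rates are equal:

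| Error, ultrasound / control | p = 40% | p = 56% | p = 70% |
|---|---|---|---|
| 0 / 0 | 2.95% | 3.16% | 2.29% |
| 10% / 0 | 4.69% | 3.89% | 2.59% |
| 20% / 0 | 9.96% | 6.34% | 3.71% |
| 30% / 0 | 19.52% | 10.83% | 5.86% |
| 20% / 10% | 4.88% | 3.58% | 2.56% |
| 30% / 20% | 4.78% | 3.24% | 2.61% |
| 30% / 10% | 10.02% | 5.95% | 3.80% |

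- With error in the ultrasound arm only, 5% is passed at m of about 10.9% (p = 40%), 15.5% (p = 56%) and 26.6% (p = 70%).
- At p = 56%, significant results favouring ultrasound alone go from 1.58% with no error to 3.23, 6.10 and 10.76% at m = 10, 20 and 30%.
- Equal error of 10, 20 or 30% in both arms gives 2.92, 2.61 and 2.32% at p = 56%. At p = 40% it gives 3.1 to 3.3%, slightly above the 2.95% without error but still below 5%.

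**Step 4: error in the control arm only.** This works against ultrasound. At p = 56%, false wins for ultrasound fall from 1.58% to 0.66, 0.24 and 0.08%. With an assumed true effect of 93% versus 56%, power falls from 81.8% to 72.1, 60.3 and 46.8% at m = 10, 20 and 30%.

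**Step 5: scale.** From 56%, 25 per arm reaches about 80% power at 92.5% success (79.9%), a difference of 36.5 points. Shifts of 4.4, 8.8 and 13.2 points are 12, 24 and 36% of that.

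**The case against.** The case on the other side has four parts.

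1. *The point rests on silence.* The protocol never says the operator is the recorder, and section 3.3 does not bar the assistant from outcome work. Both statements are correct. However, section 3.7 does allocate all outcome recording, so this is a stated rule and not a detail left for later. The objection limits the wording to self-recording being not excluded.
2. *Protections exist.* Success has written criteria, aspiration of blood is close to binary, and forms are completed in real time. A falsely recorded success would also tend to surface as early catheter loss or a later central line or PICC, both of which are secondary outcomes. This carries weight for success, but it does not verify the puncture count or the time.
3. *The arithmetic is mild.* Passing 5% needs error concentrated in one arm or a wide gap between arms, and nothing in the protocol shows arm-specific error. This stands, and it is why no threat to validity is claimed.
4. *The remedy is partial.* The assistant is unblinded too, cannot feel resistance, and would have to attend procedures while also enrolling in a 33-bed unit. This also stands. The gain is largest for puncture count and time, and time is compared in section 3.8 without being listed as an outcome in section 3.6.

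**Conclusion.** The concern holds as a design weakness that should be corrected. The protocol assigns all outcome recording in an open trial to participating nurses, does not separate recorder from operator, and names no outcome role for an assistant who is already available for data collection.

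Observer bias in success, puncture count and time is possible, but its direction and size are unknown. Under the assumed error rates at 56% true success, the false-positive rate for the primary outcome ranges from no inflation (equal error) to 10.8% (30% error in the ultrasound arm only). Error confined to the control arm would instead cost power. Confidence is medium, because the operator's role in completing the form is a natural reading and not a stated fact.

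**What to change.** Amend section 3.7 and section 4 as follows.

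- For patients enrolled during the assistant's hours, the research assistant, not the operator, counts and records each skin puncture after randomization, the start and stop times, and the success criteria that can be seen: blood aspirated, flush completed, visible extravasation.
- Resistance to flush is recorded as the operator's report.
- The form states who recorded the outcome. For any patient enrolled outside those hours, no second nurse is required; this entry is enough.
- 24-hour catheter survival, later complications and later PICC or central line stay with the nurses.

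The cost is wording in two sections and one line on the form, with no new staff and no change to sample size, alpha or power. The assistant must stay through each procedure they record; the target of 2 × 25 = 50 patients bounds that workload. Because the assistant also knows the allocation, bias is reduced and not removed.

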### ***3.8. Data analysis***

An intention-to-treat analysis will be performed. Using the power of 80% and alpha of 0.05, the sample size was calculated to be 25 per group. Categorical variables such as success rate, catheter survival rate and complication rate will be presented as a percentage and will be compared using Fisher exact tests. Continuous variables such as insertion time and the number of attempts will be shown as mean, median (with interquartile ranges), and 95% confidence interval (CI) and will be compared using Mann-Whitney U tests. All statistical analysis will be conducted using IBM SPSS Base 25 for Windows.

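### Fisher's exact test at 25 per arm is valid but uses at most 3.3% of the 5% alpha; an exact unconditional test would recover some power, by an amount that depends on control success

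*Protocol*

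**What the plan says.** The primary outcome in protocol section 3.6 is binary: "Successful cannulation by ICU nurses". Section 3.8 gives the design in one sentence: "Using the power of 80% and alpha of 0.05, the sample size was calculated to be 25 per group". It states no success rates, effect size, sidedness or calculation method.

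Section 3.8 then says that categorical variables, with success rate listed first, "will be presented as a percentage and will be compared using Fisher exact tests". Continuous variables, by contrast, "will be shown as mean, median (with interquartile ranges), and 95% confidence interval (CI"). All analyses are assigned to IBM SPSS Base 25.

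The only pair of success rates for nurse-performed access in difficult patients is in section 2, where an emergency-department trial is reported to have found a "higher success rate of 76% in placing a functional IV compared to 56% using the standard palpation technique". The protocol does not tie that pair to its sample size.

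**The concern.** Fisher's test conditions on the total number of successes as well as on the arm sizes. With 25 per arm, few tables are possible for any given total. The test can therefore rarely be run close to 5%, and its real error rate falls well below the alpha the plan allows. The unused alpha is lost power, and a 50-patient trial has little to spare.

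In practice some results that this trial could plausibly see would be declared non-significant under the written plan, although another exact test that also holds 5% would reject. One example is 21/25 against 14/25, an observed benefit of 28 points.

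**Working it through.** **Inputs.** From section 3.8: alpha 0.05, power 80%, n = 25 per group, Fisher's exact test. From section 2: 56% vs 76%, and a success rate above 88% after 15 to 26 attempts; section 3.5 requires at least 15 successful procedures per nurse, which makes 88% a relevant ultrasound rate. Assumptions: two-sided testing, 1:1 allocation, independent binomial counts in each arm. All other rates below are illustrative.

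**The plan's own figure.** 25 per group cannot be reproduced, because no rates are given. For orientation, the usual formula is

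n = [1.96·√(2·p̄(1−p̄)) + 0.842·√(p₁(1−p₁) + p₂(1−p₂))]² / (p₂−p₁)².

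At 56% vs 76%, p̄ = 0.66 and n = [1.96·√0.4488 + 0.842·√0.4288]² / 0.04 ≈ 87 per arm. About 25 per arm fits pairs such as 50% vs 86%, 56% vs 90% or 30% vs 69%.

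**Step 1: true size.** List all 26 × 26 = 676 outcome tables and mark those with two-sided Fisher p ≤ 0.05. For a common success rate p, size(p) = Σ Bin(i; 25, p)·Bin(j; 25, p) over the marked tables.
- Fisher: 362 tables reject. The maximum size is 3.28%, at p = 0.50. At p = 0.30 or 0.70 the size is 2.3%.
- Boschloo: use Fisher's p-value as the statistic and take the largest cut-off whose maximum size stays at or below 5%. That cut-off is 0.0792. The maximum size is 4.63%, and 386 tables reject.
- The Boschloo region contains every Fisher table plus 24 more. Among the extra tables are 22/25 vs 15/25 (Fisher p = 0.0507), 21/25 vs 14/25 (0.062) and 20/25 vs 13/25 (0.072).

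**Step 2: power.** Sum Bin(i; 25, p₁)·Bin(j; 25, p₂) over each rejection region.

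| Control vs ultrasound | Fisher | Boschloo | Gain (points) |
|---|---|---|---|
| 56% vs 76% (cited) | 22.8% | 31.0% | 8.1 |
| 56% vs 88% | 61.7% | 72.0% | 10.3 |
| 56% vs 90% | 69.8% | 78.8% | 9.0 |
| 50% vs 80% | 51.0% | 60.6% | 9.6 |
| 50% vs 85% | 67.6% | 76.8% | 9.3 |
| 60% vs 90% | 59.1% | 69.0% | 9.9 |
| 40% vs 60% | 23.7% | 25.1% | 1.4 |
| 40% vs 80% | 78.8% | 83.3% | 4.5 |
| 30% vs 60% | 50.6% | 53.5% | 2.9 |
| 30% vs 70% | 78.2% | 79.3% | 1.1 |

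Gains are taken before rounding. Even with control success at 50-60%, the gain is smaller at the ends of the range: 4.9 points at 50% vs 70% and 5.3 at 60% vs 95%. It peaks at about 11, at 56% vs 86%.

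**Step 3: precision.** At the cited rates the approximate 95% half-width for the risk difference is 1.96·√(0.76·0.24/25 + 0.56·0.44/25) = 0.257, or about 26 points.

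**The case against.** The strongest reply is that nothing here is wrong. Fisher's test is prespecified, holds the type I error below the stated alpha and contradicts nothing else in the protocol. That stands: the point is about efficiency.

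Second, under randomisation-based inference with fixed arm sizes, a strict null of no effect fixes the total number of successes, and Fisher's test is then the natural exact test. Section 3.3 describes a convenience sample, which makes that view reasonable. Boschloo's guarantee needs the binomial model. This limits the claim but does not remove the gain under that model.

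Third, the size of the gain. A reader might infer a general loss of 8 to 10 points. The documents do not support that, because no design rates are stated. Patients enter only after two failed attempts, so landmark success below 50% is plausible, although up to three further attempts count towards it. At 30-40% the gain is small.

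A reader might also infer that the planned 80% power is really 67% to 69%. That would require the sample size to have come from an uncorrected chi-square calculation at particular rates (56% vs 89.4%, or 50% vs 85.4%). The protocol gives neither the method nor those rates. At 40% vs 80% or 30% vs 70%, Fisher's test itself has 78-79% power, close to the stated figure.

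Finally, the missing interval for the primary outcome carries little weight. A statistical analysis plan commonly supplies one, and a reader could compute it from the percentages and arm sizes.

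**Conclusion.** The point holds as a cheap improvement. At 25 per arm the named test cannot use more than 3.3% of its 5%. Boschloo's test stays within 5% (maximum 4.6%) and, at this sample size, rejects every table that Fisher's rejects, so under binomial sampling it cannot lose power. The gain is about 8 to 10 points for mid-range effects if control success is near 50-60%, and about 1 to 5 points at 30-40%.

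The figures assume two-sided testing, exactly 25 analysed per arm and independent binomial outcomes. The change does not repair the design: at the cited 56% vs 76%, power is 31% even with the better test. The absence of design rates behind the sample size is a separate and larger weakness.

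**What to change.** Before outcome data are analysed, amend section 3.8 along these lines: *The primary outcome will be compared with Boschloo's exact unconditional test at the two-sided 5% level. The main result will be the risk difference (ultrasound minus landmark) with a 95% score-type or exact confidence interval. Fisher's exact p-value will be reported as a sensitivity result.*

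No extra patients are needed. There are three costs:
- The test rests on a binomial sampling model, which should be stated.
- The protocol assigns all analyses to SPSS Base 25 and does not say whether that package offers the test. A second package may be needed, and the software sentence would then have to change too.
- The protocol dates enrolment from December 2018 to May 2019 and the trial is unblinded. If outcome results by arm have already been examined, Fisher's test should remain primary, with only the interval added.

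### Do insertion time and 24-hour catheter survival leave out failed cannulations, against the stated intention-to-treat analysis?

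*Protocol*

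**What the plan says.** Section 3.8 sets one principle for the whole analysis, "An intention-to-treat analysis will be performed", and makes no exception for any outcome. It then divides the outcomes by type. For the first group, "Categorical variables such as success rate, catheter survival rate and complication rate will be presented as a percentage", the comparison is by Fisher exact test. For the second, "Continuous variables such as insertion time and the number of attempts will be shown as mean, median (with interquartile ranges", it is by Mann-Whitney U test.

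Section 4 says that time is recorded in minutes by the nurse in real time, "with time zero defined as the first skin puncture after patient randomization in the study". It names no stop event. The same section defines failed cannulation as three failed attempts after the two that made the patient eligible.

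Section 3.6 lists "24 hours catheter survival" as a secondary outcome without a denominator. Insertion time does not appear in the section 3.6 list; it is met only in sections 3.8 and 4.

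**The concern.** A time to insertion and the survival of a catheter are most naturally thought of as existing only once a catheter is in. If the time field is left blank for a failed patient, a Mann-Whitney test skips that patient. If survival is counted among placed catheters, the failed patients leave the denominator. Both comparisons would then be conditioned on success, which is the primary outcome and which the trial expects to differ between the groups. The ultrasound subset would include harder patients in whom the landmark technique would have failed, so the groups compared would no longer be the randomised ones.

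The direction of a result could then depend on an unstated choice, in an unblinded trial. The literature review gives this some plausibility for survival: "Deep veins (depth > 1.2 cm) and proximal location were associated with early catheter failure" when ultrasound guidance was used. Ultrasound could look worse on catheter survival while leaving more randomised patients with a working line.

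**Working it through.** **Inputs.** The group size comes from section 3.8: "Using the power of 80% and alpha of 0.05, the sample size was calculated to be 25 per group". That figure cannot be reproduced, because no effect size is given with it, but the present point does not depend on it. For success rates I take the nurse trial in the literature review, whose ultrasound arm "had a higher success rate of 76% in placing a functional IV compared to 56% using the standard palpation technique". The protocol does not tie these rates to its own design, so they are an assumption. Survival rates and times per attempt are also assumptions.

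**Patients at stake if failures were dropped.**
- Successes: 25 × 0.76 = 19 ultrasound and 25 × 0.56 = 14 landmark.
- Failures: 6 and 11, together 17 of 50 (34%).

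**Survival.** Working catheter at 24 hours among all randomised = P(success) × P(survival given success).
- The two denominators disagree in direction when ultrasound survival among placed catheters is below landmark survival, but 0.76 × ultrasound survival exceeds 0.56 × landmark survival. That is a ratio between 0.56/0.76 = 0.737 and 1.
- Example: 16/19 (84%) against 13/14 (93%) favours landmark. Over all randomised, 16/25 (64%) against 13/25 (52%) favours ultrasound.
- Fisher p-values for these two tables are 0.62 and 0.57. Neither would support a conclusion in either direction.

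**Insertion time.** Assumed model: up to three attempts, with success per attempt 1 − (1 − 0.76)^(1/3) = 0.379 for ultrasound and 1 − (1 − 0.56)^(1/3) = 0.239 for landmark. Time per attempt is lognormal with median 3 minutes and log-SD 0.5, and an ultrasound attempt takes a multiple of that time. The table gives the simulated chance that an ultrasound patient is faster than a landmark patient.

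| Ultrasound time multiple | Successes only | All 50, failures ranked last | All 50, failures at their observed time to the third attempt |
|---|---|---|---|
| 1.25 | 44% | 57% | 48% |
| 1.5 | 36% | 54% | 40% |

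The direction changes only in the middle column. Keeping every randomised patient at the time actually observed leaves the result on the same side of 50% as the successes-only analysis. The reversal therefore comes from ranking failures last, which brings the success difference into the time outcome. It does not come from analysing all randomised patients.

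Power shows the same dependence on the rule. With equal times per attempt it is 6% on successes only and 29% with failures ranked last, part of that gain being the success difference. At a multiple of 1.5 the order turns round: about 24% on successes only (towards landmark) and about 9% with failures ranked last.

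**Does the text drop anyone?** No section restricts either outcome to successful cannulations. Section 3.8 puts catheter survival in the same list as success rate, under the same test and the same intention-to-treat sentence. The reading that fits is one denominator, all randomised, with a failed patient counted as having no surviving catheter. For time, section 4 supplies both a start and, through its definition of failure, a natural end at the third failed attempt.

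**The case for a change.** The strongest reply is that the protocol has a definitions section which fixes the start of the clock and stops there. The nurse fills in the time at the bedside. If forms are completed to different end points, or left blank after failure, an analysis plan written later cannot recover the values. An open survival denominator also leaves room for a choice once results are seen, and nobody is blinded. The clarification would cost only a few sentences.

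Part of this stands. The stop event is unwritten, and a line on the data form saying when to stop the clock would be good practice. If failed patients were in fact left out, the two comparisons would conflict with the intention-to-treat sentence.

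It does not carry further than that. The conflict arises only on a reading that the intention-to-treat sentence itself rules out. How failures are ranked and which denominator each secondary outcome uses are commonly settled in a statistical analysis plan, which may exist but is not shown. Nor is there one right answer to impose. Ranking failures last makes time partly repeat the primary outcome and empties the promised mean and confidence interval of meaning, while survival among placed catheters is a legitimate question about durability.

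**Conclusion.** No change to the plan follows. The protocol leaves the end of insertion time and the survival denominator unwritten, but it does not exclude failed patients, and its intention-to-treat statement points to including all 50.

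The possible loss of 17 of 50 patients rests on borrowed success rates of 76% and 56% and on a restriction that the text does not contain. The reversal in insertion time is produced by the worst-rank rule: with observed times kept for all patients, the chances are 48% and 40%, against 44% and 36% among successes. The survival reversal is arithmetically possible for ratios between 0.737 and 1, but the illustrative counts give p = 0.62 and 0.57, and the survival figures are assumed.

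The gap touches one of four secondary outcomes and one measure that is not in the outcome list. The Fisher test of the primary outcome is unaffected. This is missing detail that analysts can fill sensibly, combined with a choice of estimand on which reasonable statisticians differ.
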